8.2.5.1.1. Unscheduled Visits (Unplanned Visits)

A listing will be generated for all of the subjects with unscheduled visits (or unplanned visits) for severe reactions.

8.2.5.2. Safety Data Collected Through CRF

8.2.5.2.1. SAE

The percentage of subjects reporting at least one SAE, and the number of episodes will be summarized for each group for each of the first 7 analysis intervals ([Section 6.2.3.1](#)) with 95% exact confidence intervals for the percentages. Proportion differences (between rLP2086 dose groups and HAV/saline control group), associated 95% CIs and p-values from Fisher's exact test will be provided for analysis intervals 'During the vaccination phase' and 'Throughout the AE collection period (Visit 1 to Visit 8)'.

Similarly, the percentage of subjects reporting at least one related SAE, total # of related SAEs reported by each group. No between-group proportion differences, associated CIs or p-values for comparisons between groups will be generated for related SAEs.

In addition, for analysis interval throughout the AE collection period (Visit 1 to Visit 8), the SAEs will be summarized by each preferred term (MedDRA) with percentage and number of events for each group. Listings of related SAEs will be provided.

All of the SAE will be listed with subject ID, event onset, the most recent vaccination, days of event relative to vaccination date, causality, duration of the event, and management and outcome.

8.2.5.2.2. Newly Diagnosed Chronic Medical Condition (NDCMC)

The percentage of subjects reporting at least one newly diagnosed chronic medical conditions, and the number of episodes will be summarized, by severity and overall, for each group for each of the first 7 analysis intervals with 95% Clopper-Pearson CI for the percentages. Proportion differences (between rLP2086 dose groups and HAV/saline control group), associated 95% CIs and p-values from Fisher's exact test will be provided for analysis intervals 'During the vaccination phase' and 'Throughout the AE collection period (Visit 1 to Visit 8)' for any severity.

Similarly, the percentage of subjects reporting at least one related newly diagnosed chronic medical condition, and total # of related newly diagnosed chronic medical conditions will be reported by each group. No between-group proportion differences, associated CIs or p-values will be generated for related newly diagnosed chronic medical conditions.

In addition, for the analysis interval throughout the AE collection period (Visit 1 to Visit 8), the NDCMCs will be summarized by each preferred term (MedDRA) with percentage and number of events for each group.

8.2.5.2.3. Neuroinflammatory and Autoimmune Conditions

A list of preferred terms (MedDRA), to include all of the neuroinflammatory and autoimmune conditions, will be provided by the medical monitor prior to database lock. These events can be an SAE or AE.

A listing of neuroinflammatory and autoimmune conditions matching this preferred terms list will be provided.

8.2.5.2.4. Medically Attended Events (MAE)

The Medically attended AE will be analyzed as per [Section 8.2.5.2.1](#) in addition there will be:

- An analysis to include the summary of medically attended AE by severity for each analysis interval.
- An analysis to include 'moderate and severe' medically attended AE summary by preferred term for the analysis intervals 5 to 7.
- Proportion differences (between rLP2086 dose groups and HAV/saline control group), associated 95% CIs and p-values from Fisher's exact test will be provided for analysis intervals 'During the vaccination phase' and 'Throughout the AE collection period (Visit 1 to Visit 8)' for any severe conditions and any severity.

8.2.5.2.5. Immediate AE

The number and percentage of subjects reporting adverse events during the protocol specified first 30-minute observation period will be summarized by randomization group for each vaccination.

This immediate AE report will be summarized for each vaccination and any vaccination. These summaries will include 95% Clopper-Pearson's CI. Unconditional exact 95% CI on the proportion differences and p-value will also be provided for the analysis interval 'Within 30 days of any vaccination'.

The immediate AE categorized as SAE (defined as immediate AE and also meet the definition of SAE) will be listed.

8.2.5.2.6. AE

The AEs will be analyzed similar to SAE, except that only the first 5 intervals are applicable as non-serious AEs (except MAEs and non-serious NDCMCs) are only collected during the vaccination phase.

Non-serious AEs are not required to be reported during the follow-up phase, however, if non-serious AEs during the follow-up phase were recorded in the database (excluding MAEs and non-serious NDCMCs), these data will be listed separately.

Note that for the analysis interval of vaccination phase the AEs will be summarized by each preferred term (MedDRA) with percentage and number of events for each group. Percentages and 95% CIs on the proportion differences will also be provided when at least 4 subjects have an adverse event for a specific preferred term in any of the displayed vaccine groups.

In addition, related AEs will also be summarized by each preferred term with percentage and number of events for each group.

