5.3. Safety Analysis Set

The safety population will be used for all safety analyses. The safety population will include all subjects who have received at least 1 dose of an investigational product (bivalent rLP2086 or control) and for whom safety data are available. For the safety analysis, subjects will be analyzed according to the investigational product received.

Separate safety populations will be defined for each vaccination visit: vaccination visit 1, vaccination visit 2, vaccination visit 3, and follow-up phase for stage 1.

1. Vaccination 1 Safety Population: This population will include all subjects who received the first dose of investigational product (bivalent rLP2086 or HAV) at visit 1, and for whom safety information from visit 1 to prior to visit 4 is available.
2. Vaccination 2 Safety Population: This population will include all subjects who received the investigational product (bivalent rLP2086 or saline) at visit 4, and for whom safety information from visit 4 to prior to visit 6 is available.
3. Vaccination 3 Safety Population: This population will include all subjects who received the investigational product (bivalent rLP2086 or HAV) at visit 6, and for whom safety information from visit 6 up to visit 7 is available.
4. Follow-up Safety Population for Stage 1: This population will include all subjects who received at least 1 dose of investigational product (rLP2086 or HAV vaccine or saline) and for whom safety information is available from after visit 7 to up to visit 8. Subjects who receive the wrong investigational product and are followed for 6-month safety will not be included in this population.

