6.2.3.1. Analysis Intervals

There will be up to 7 analysis intervals for most of the safety data collected via CRF.

Table 8. Analysis Interval for AE, SAE, Medically Attended Events (MAEs), Newly Diagnosed Major Conditions (NDCMC)

#	Analysis Interval	Analysis Population	Interval Start date (inclusive)	Interval Stop (inclusive)	Safety Data
1	Within 30 days of vaccination 1	Vax 1 Safety	Vax 1 date	Vax 1 date + 30 days	AE, SAE, MAE, NDCMC
2	Within 30 days of vaccination 2	Vax 2 Safety	Vax 2 date	Vax 2 date + 30 days	AE, SAE, MAE, NDCMC,
3	Within 30 days of vaccination 3	Vax 3 Safety	Vax 3 date	Vax 3 date + 30 days	AE, SAE, MAE , NDCMC
4	Within 30 days of any vaccination	Safety	Vax 1, Vax 2, or Vax 3 date	Vax 1, Vax 2, or Vax 3 date + 30 days	AE, SAE, MAE, NDCMC,
5	During the vaccination phase	Safety	Visit 1 date	Visit 7 date (or end of vaccination day)	AE, SAE, MAE, NDCMC
6	During the follow-up Phase (Stage 1)	Follow-up Stage 1	Visit 7 date + 1 day, or end of vaccination date + 1 for early withdrawal subjects	Visit 8 date	SAE, MAE, NDCMC,
7	Throughout the AE collection period (Stage 1)	Safety	Visit 1 date	Visit 8 date	SAE, MAE, NDCMC, autoimmune and neuroinflammatory conditions

AE=Adverse events, SAE=serious adverse events, MAE=Medically-attended AE, NDCMC=Newly diagnosed chronic medical conditions

Four (4) analysis intervals will be applied to immediate AEs.

Table 9. Analysis Interval for Immediate AE

#	Analysis Interval	Analysis Population	Interval Start date (inclusive)	Interval Stop (inclusive)
1	vaccination 1	Vax 1 Safety	Vaccination 1 time	Vaccination 1 time + 30 minutes
2	vaccination 2	Vax 2 Safety	Vaccination 2 time	Vaccination 2 time + 30 minutes
3	vaccination 3	Vax 3 Safety	Vaccination 3 time	Vaccination 3 time + 30 minutes
4	any vaccination	Safety	Vaccination 1, 2, or 3 time	Vaccination 1, 2, or 3 time + 30 minutes

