6.2.3.2. Immediate Adverse Events

Any AE that occurred within the first 30 minutes after the investigational product administration will be classified as an immediate AE.

Immediate AEs are a subset of AEs.

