The partial date in above example will be imputed as ‘2012-01-17’, the day of the second vaccination date.

B2. If the AE start month is not the same as the subsequent dose month: Stop here and keep the original **1st day of the month as imputed date.**

AE	AE Start Date	AE Stop Date	Date of Dose 1	Date of Dose 2	Date of Dose 3
Common cold	2012-03	2012-04	2011-10-10	2011-12-05	2012-04-12

The partial date in above example will be imputed as ‘2012-03-01’, the first day of the month.

Partial missing date with only year available:

The imputation approach will be the same as the missing day.

1. If AE partial date indicates AE start date is prior to first dosing date, **no imputation** is needed since it can be slotted as ‘prior to vaccination phase’.

AE	AE Start Date	Date of Dose 1	Date of Dose 2	Date of Dose 3
Depression	2011	2012-01-05	2012-02-24	2012-06-14

2. If AE partial date could not determine if AE start date is prior to first dosing date, impute day to January 1st of the year and compare the imputed AE start date with the earliest dosing date in the same calendar year and AE stop date.2.1. Compare the stop date with the earliest dosing date in that calendar year, if the stop date is earlier than the earliest dosing date in the same calendar year, the AE start date will remain the **first day of the calendar year**

AE	AE Start Date	AE Stop Date	Date of Dose 1	Date of Dose 2	Date of Dose 3
Common cold	2012	2012-01-12	2011-11-23	2012-02-08	2012-06-13

The partial date in above example will be imputed as ‘2012-01-01’, the first day of the year.

- 2.2. Compare the stop date with the earliest dosing date in that calendar year, if the stop date is later than the earliest dosing date in the same calendar year, the AE start date will be imputed as the **earliest dosing date in that calendar year**

AE	AE Start Date	AE Stop Date	Date of Dose 1	Date of Dose 2	Date of Dose 3
Common cold	2012	2012-06-12	2011-11-23	2012-02-08	2012-06-13

The partial date in above example will be imputed as ‘2012-02-08’, the earliest dosing date in calendar year 2012.

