10.1.1.4. Summary

With above imputation method, the most conservative approach was used. Therefore, if no apparent indication from the stop date and the part start date, the AE can be slotted to any of the primary endpoint analysis interval (within 30 days of vaccination). In addition, these events will be slotted to the vaccination phase, given the event is either imputes to the date of a vaccination day of the 1st day of the month (or year).

To be specific, 2.2.B1 (missing day) and case 2.2 (missing month and day) in [Section 10.1.1.3.2](#) will be allocated to **AE within 30 days after dose 2**.

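### SAP 10.1.1.4 allocates two classes of partly dated AEs to dose 2 even when their dates are imputed to another dose; the immediate-AE section also names the wrong interval and grouping.

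*SAP*

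**What the plan says.** **Partial AE start dates.** SAP 10.1.1.3.2 gives branch-by-branch rules. When only the day is missing and branch 2.2.B1 applies, the start becomes the date of the subsequent dose. When only the year is known, the programmer is to "compare the imputed AE start date with the earliest dosing date in the same calendar year and AE stop date". In case 2.2, where the AE stops after that dose, the start becomes that dose date. SAP 10.1.1.4 first says that such AEs can fall in any of the 30-day post-dose intervals. It then names "2.2.B1 (missing day) and case 2.2 (missing month and day") and assigns both to the 30-day interval after dose 2. SAP 10.1.2.2.2 repeats that these AEs go to various intervals. It adds that an AE imputed to a vaccination day is not to be placed in an interval before that vaccination.

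**Immediate AEs.** SAP 6.2.3.1 states "Four (4) analysis intervals will be applied to immediate AEs". Table 9 row 4, for any vaccination, ends at "Vaccination 1, 2, or 3 time + 30 minutes". In SAP 8.2.5.2.5, however, the exact CI on the difference and the "p-value will also be provided for the analysis interval 'Within 30 days of any vaccination". That is the label of Table 8 row 4, which covers AEs, SAEs, MAEs and NDCMCs.

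**Grouping.** SAP 8.2.5.2.5 says that events in the 30-minute "observation period will be summarized by randomization group for each vaccination". SAP 5.3 says "For the safety analysis, subjects will be analyzed according to the investigational product received", and Protocol 9.2 has the same rule.

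**The concern.** AEs within 30 days of each vaccination, and immediate AEs, are primary safety endpoints (Protocol 2.2.2, SAP 6.2.1). SAP 2 says the windowing specifications and programming rules are prepared from this document, so a sentence that contradicts the rule it summarises may be coded as written.

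For the two named partial-date branches, the dose used for imputation need not be dose 2. Forcing the AE into the dose 2 interval credits it to a dose the imputation did not choose. In the control arm this also changes the product, because dose 2 is saline and doses 1 and 3 are HAV vaccine (Protocol Table 6). A child who never received dose 2 is not in the Vaccination 2 Safety Population, so an AE of that child sent to dose 2 has no valid place in the by-dose table.

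The two slips in the immediate-AE section matter less. They leave the event set and the grouping open to a reading that the rest of the SAP does not intend.

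**Working it through.** **1. Reproduce the SAP's own examples.** SAP 10.1.1.3.2 has six worked examples that give an imputed date. Applying the written rules reproduces all six. The two that matter here are:

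- 2.2.B1: start 2012-01, stop 2012-02-17, doses 2011-11-22, 2012-01-17 and 2012-05-09. The provisional date 2012-01-01 is after dose 1. The next dose is 2012-01-17, in the same month, and the AE stops after it. Imputed: 2012-01-17, which is dose 2.
- Year-only 2.2: start 2012, stop 2012-06-12, doses 2011-11-23, 2012-02-08 and 2012-06-13. The earliest dose in 2012 is 2012-02-08, before the stop. Imputed: 2012-02-08, which is dose 2.

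**2. Apply the same rules to other AEs.** The dose dates below are the SAP's own; the AE start and stop dates are mine.

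| Branch | AE start / stop | Doses 1, 2, 3 | Imputed to | Days from dose 2 |
|---|---|---|---|---|
| 2.2.B1 | 2012-05 / 2012-05-20 | 2011-11-22, 2012-01-17, 2012-05-09 | dose 3 | +113 |
| 2.2.B1 | 2012-04 / 2012-04-20 | 2011-10-10, 2011-12-05, 2012-04-12 | dose 3 | +129 |
| Year-only 2.2 | 2012 / 2012-02-17 | 2012-01-05, 2012-03-01, 2012-06-13 | dose 1 | −56 |
| Year-only 2.2 | 2011 / 2011-12-20 | 2011-11-23, 2012-02-08, 2012-06-13 | dose 1 | −77 |

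None lies between 0 and 30 days after dose 2, yet 10.1.1.4 assigns all four there. (The SAP's illustrative dates do not all respect this protocol's visit windows.)

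**3. Use the protocol's windows.** Dose 3 is due 105 to 126 days after dose 2 (Protocol 6.1.6). The dose 2 interval closes at day 30, so it has been closed for 105 − 30 = 75 to 126 − 30 = 96 days when dose 3 is given. Placing a dose 3 AE there breaks 10.1.2.2.2. Dose 2 is due 42 to 70 days after dose 1 (Protocol 6.1.4), so an AE imputed to dose 1 precedes the dose 2 interval by 42 to 70 days. That conflicts with Tables 8 and 11, which allocate by date.

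**4. Which analyses can change.** An AE imputed to any dose date is within 30 days of a vaccination and inside the vaccination phase, so rows 4 and 5 of Table 8 are the same under either rule. SAP 8.2.5.2.1 limits differences and p-values to the vaccination phase and the whole AE collection period, and 8.2.5.2.6 analyses AEs in the same way. This leaves rows 1 to 3 of Table 8, which carry percentages and within-group CIs only.

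**5. How the branches split (illustration).** Assume dose 1 uniform over a calendar year, onset uniform from dose 1 to Visit 7, and mean AE duration of 7 to 30 days. Simulation with the stop-date condition then gives:

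- 2.2.B1: about 49% to dose 2 and 49% to dose 3.
- Year-only 2.2: 77–80% to dose 1, 13% to dose 2 and 7–10% to dose 3.

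These are shares of each branch, not of all AEs.

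**6. Immediate AEs.** SAP 6.2.3.2 says "Immediate AEs are a subset of AEs". An event within 30 minutes of a vaccination is necessarily within 30 days of it. So the flagged immediate AEs that fall in Table 8 row 4 are exactly those in Table 9 row 4. Both rows use the Safety population. With the flag applied, numerator, denominator, CI and p-value are identical. Only if the named interval replaces the flag would all 30-day AEs be compared.

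**The case against.** The best defence of 10.1.1.4 is that it is headed as a summary, follows a sentence allowing any post-dose interval, and refers to branches whose worked examples both land on dose 2. It may have been meant to describe those examples. That is possible, but the text names the branches, not the examples, and states an allocation. One could also read the subsequent dose in 2.2.B1 as always being the one after dose 1. That would rescue 2.2.B1, but it would leave an AE starting in the month of dose 3 without the conservative treatment that 10.1.1.3 promises, and it does nothing for the year-only case.

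Other parts of the defence stand. Only two branches are involved: completely missing dates and month-year case 2.1 go to dose 1, and 2.2.A, 2.2.B2 and year-only 2.1 keep the first day of the month or year. AE dates are queried, so year-only dates should be rare.

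A reader might infer from 8.2.5.2.5 that the immediate-AE contrast is really a contrast of 30-day AEs. The documents do not support that. The sentence sits under the immediate-AE heading, and SAP 8.1.2.2 assigns the unconditional exact method to immediate AEs and Fisher's test to AEs generally. A reader might also infer that the comparison itself is made by randomised group; the phrase belongs to the per-vaccination summary.

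**Conclusion.** The point holds as an internal contradiction with a narrow reach. Read literally, 10.1.1.4 misplaces AEs from 2.2.B1 whenever the dose used is dose 3, and AEs from year-only case 2.2 whenever it is dose 1 or dose 3. The error is confined to the descriptive by-dose 30-day summaries. It would be wrong to conclude that partly dated AEs in general are sent to dose 2, or that a planned between-group AE comparison is affected. The documents do not say how many AEs will have such dates. I assume few, and the branch shares above do not measure impact on the AE rates.

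The interval label in 8.2.5.2.5 is wrong against Table 9 but changes no count once the immediate-AE flag is used. The randomization wording conflicts with SAP 5.3 and Protocol 9.2, and matters only for children given the wrong product or vaccinated without randomisation. SAP 5.5 reports the latter under the vaccine received, and they would have no group here.

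**What to change.** Make three wording changes in the SAP:

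1. In 10.1.1.4, replace dose 2 with the dose whose date was used for the imputation. This works under either reading of the subsequent dose.
2. In 8.2.5.2.5, replace the 30-day interval with Table 9 row 4, any vaccination (30 minutes).
3. In the per-vaccination summary of 8.2.5.2.5, replace randomization group with vaccine received.

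No new data, analyses or protocol amendment are needed. The windowing and programming specifications should be checked once against the corrected text.

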8.2.5.2.7. Multiple Events per Subject (Incidence Rates)

The frequency distribution on number of events reported by each subject will be summarized for each of the following safety variables:

1. Any AE during the vaccination phase.
2. Any SAE throughout the AE collection period (Visit 1 to Visit 8),
3. Any medically attended AE throughout the AE collection period (Visit 1 to Visit 8).
4. Any newly diagnosed chronic medical conditions throughout the AE collection period (Visit 1 to Visit 8).
5. Any newly diagnosed chronic medical conditions categorized as throughout the AE collection period (Visit 1 to Visit 8).

For each subject, the number of events reported per year will be estimated by summarizing the total number of events reported over the observation period and standardizing it to an annual rate by multiplying by 365 and dividing by days on study. The overall incidence rate (including 95% confidence intervals) for each of the safety variables will be reported by group.

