3.5. Expanded-Enrollment Phase

3.5.1. 12- to <18-Month Age Stratum

The IRC will review all post–Vaccination 1, 7-day e-diary and AE data obtained from sentinel subjects aged 12 to <15 months. Based on the review, the IRC will select the bivalent rLP2086 dose level to be studied in the Stage 1 expanded-enrollment phase. Younger-age sentinel subjects cannot participate in the 120-µg dose level before the safety data of the 120-µg dose level have been found to be acceptable in the 120-µg older-age sentinel cohort.

The expanded-enrollment phase for this age group will enroll approximately 132 subjects: 66 aged 12 to <15 months and 66 aged 15 to <18 months. Within each of these substratified age groups, subjects will be randomly assigned in a 2:1 ratio to the selected dose level of bivalent rLP2086 or HAV vaccine/saline.

In the event that neither dose level is considered to exhibit a satisfactory safety profile for the 12- to <15-month age group sentinel cohort, expanded enrollment will not commence in the 12- to <18-month age group. So that the study may meet its enrollment numbers, additional enrollment will be permitted in the 18- to <24-month age group.

3.5.2. 18- to <24-Month Age Stratum

The IRC will review all post–Vaccination 1, 7-day e-diary and AE data obtained from sentinel subjects aged 18 to <24 months. Based on the review, the IRC will select the bivalent rLP2086 dose level to be studied in the Stage 1 expanded-enrollment phase.

Once the dose level is selected, an additional approximately 132 subjects aged 18 to <24 months will be enrolled. Subjects will be randomly assigned in a 2:1 ratio to the selected dose level of bivalent rLP2086 or HAV vaccine/saline.

B1971035

Final Protocol Amendment 2, 19 April 2016

3.6. Progression to Stage 2

For all subjects completing Stage 1, a telephone contact will occur at Visit 10 to notify the parent(s)/legal guardian of their child's randomization allocation. Only those subjects who received the 3-vaccination series of bivalent rLP2086 (irrespective of dose level) will continue through Stage 2 to study completion. Subjects who received the 3-vaccination series of HAV vaccine/saline will conclude the study with the Visit 10 telephone contact (Section 6.1.10).

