Following completion of the sentinel data review(s) of the 120- μ g dose, either the 60- μ g dose or the 120- μ g dose will be selected for each age cohort by the IRC for use in the expanded-enrollment phase of Stage 1.

If the IRC finds the summary safety data for the 120- μ g dose to be acceptable, and no further review is warranted, the subjects in the 120- μ g sentinel cohort will continue through the vaccine series. Younger-age sentinel subjects will not progress to the 120- μ g dose level before the safety data of the 120- μ g dose level have been found to be acceptable in the older-age sentinel cohort. If the 120- μ g summary safety data are unacceptable in the younger-age sentinel cohort but acceptable in the older-age sentinel cohort, then a) vaccination and enrollment at the 120- μ g dose level will cease in the younger-age sentinel cohort, but vaccination and expanded enrollment may continue in the younger-age sentinel cohort at the 60- μ g dose level, and b) vaccination and expanded enrollment may continue at the 120- μ g dose level for the older-age sentinel cohort.

If the summary data for the 120- μ g dose are unacceptable in the older-age sentinel cohort, vaccination and enrollment for the sentinel cohort at the 120- μ g dose level will cease. Further expanded enrollment and vaccination, however, may continue at the 60- μ g dose level.

2.1.2.2. Expanded Enrollment, Stage 1

The expanded-enrollment stage will enroll approximately 132 subjects each into 2 age groups (12 to <18 months and 18 to <24 months), randomly assigned in a 2:1 ratio to the selected dose level of bivalent rLP2086 or HAV vaccine/saline. Randomization will be substratified in the younger age group only: 12 to <15 months and 15 to <18 months. The selected dose level in the expanded-enrollment phase may differ between age groups (12 to <18 months and 18 to <24 months), but not within the substratum (12 to <15 months and 15 to <18 months) of the younger age group.

2.1.2.3. Enrollment Plan, Stage 2

Those subjects who received all 3 study vaccinations of bivalent rLP2086 and who were randomly assigned to bivalent rLP2086 at either dose level may progress to the open-label Stage 2. Subjects randomly assigned to HAV vaccine/saline will not enter Stage 2. To facilitate this transition, the subject's parent(s)/legal guardian will be notified of the subject's randomization allocation at prior to entry into Stage 2.

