3.2. Primary Analysis

The primary analysis will be performed when all of the immunogenicity data through Visit 7 and all the safety data up to and including Visit 8 are available. The final analysis will include all data not reported in the first CSR and will be performed separately after all of the subjects finish the study when all of the data are available. As this study is not a hypothesis-testing study, no alpha will be adjusted on these analyses.

Interim summaries of immunogenicity and safety data may be generated to summarize key immunogenicity and safety endpoints. As this study is not a hypothesis-testing study, no alpha will be adjusted on these analyses.

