10.1.5.6.2. Dates

The 2 dates will be used to derive total subject-duration for the calculation of incidence rates.

2 subject summary pages will be provided (one for end of vaccination phase and one for end of study); therefore the 2 dates can be derived from the 2 pages.

Table 13. End of Study Date and End of Vaccination Phase Date

Study	# of Subject Summary Page	End of Vaccination Date	End of Study Date
B1971035	2	
 Visit Date for ‘Subject summary Page- Vaccination Phase’ (This date should be on the same day of last visit during vaccination phase or later) 	
 Visit Date for ‘Subject summary Page- End of Study’ (This date should either be the Visit 10 or Visit 13 date, whichever is later)

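### Incidence rates for SAEs, MAEs and NDCMCs count events to Visit 8 but divide by time on study, which ends at other dates and, for End of Study, differs by arm

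*SAP*

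**What the plan says.** SAP 8.2.5.2.7 lists five safety variables. Variable 1 is any AE in the vaccination phase. Variables 2 to 5 cover SAEs, MAEs and NDCMCs up to Visit 8; the second reads "Any SAE throughout the AE collection period (Visit 1 to Visit 8". Each subject's count is annualised by "standardizing it to an annual rate by multiplying by 365 and dividing by days on study", and an overall rate with a 95% confidence interval is reported by group.

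Person-time is defined in SAP 10.1.5.6.2: "The 2 dates will be used to derive total subject-duration for the calculation of incidence rates". Table 13 gives the two dates. End of Vaccination is the last vaccination-phase visit or later. For End of Study, "This date should either be the Visit 10 or Visit 13 date, whichever is later".

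Follow-up differs by arm. SAP 2.1.2.3 states "Subjects randomly assigned to HAV vaccine/saline will not enter Stage 2", and Protocol 3.6 states "Subjects who received the 3-vaccination series of HAV vaccine/saline will conclude the study with the Visit 10 telephone contact". Protocol 3.7 puts total participation for those who complete Stage 2 at about 54 months.

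On timing, SAP 3.2 places the primary analysis when Visit 7 immunogenicity and "all the safety data up to and including Visit 8 are available". It adds: "The final analysis will include all data not reported in the first CSR".

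**The concern.** A rate needs the same window in the numerator and the denominator. Here the events for variables 2 to 5 stop at Visit 8, while the two permitted end dates lie about five months before it or at least six months after it. The SAP does not say which date goes with which variable. Variable 1 fits End of Vaccination, which leaves End of Study as the natural choice for the others.

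That choice does not treat the arms alike. A vaccinee who completes Stage 2 adds about 36 months of denominator beyond a control who ends at Month 18, and none of that time can contribute a counted event. Equal risk would then show as a lower rate on vaccine. The primary safety objective is a comparison with control, so a group table with this property could mislead.

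There is a second gap. SAP 8.2.5.2.7 describes a rate for each subject, while SAP 10.1.5.6.2 speaks of a total duration. One suggests a mean of subject rates, the other pooled events over pooled time. They need different confidence intervals, and neither is named.

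**Working it through.** The documents give no expected rate or person-time, so there is no figure to reproduce. The check applies the SAP formula, events × 365 / days, with the same true rate in both arms up to Visit 8. The reported rate is then the true rate × (time to Visit 8) / (time in the denominator).

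**Nominal times** (Schedule of Activities; Protocol 3.7): Visit 7 at Month 7, Visit 8 at 12, Visit 9 at 18, Visit 13 at 54. Visit 10 has no window but follows Visit 9.

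| Denominator ends at | Control | Vaccine | Vaccine/control |
|---|---|---|---|
| End of Study, Visit 10 at Month 18 | 12/18 = 0.67 | 12/54 = 0.22 | 18/54 = 0.33 |
| End of Vaccination | 12/7 = 1.71 | 12/7 = 1.71 | 1.0 |
| Visit 8 | 1.0 | 1.0 | 1.0 |

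In the first row a true threefold excess on vaccine (54/18) would look like no difference.

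**Visit windows.** In days from Visit 1:
- Visit 6: 42+105 to 70+126 = 147 to 196.
- Visit 7: 28 to 42 days after Visit 6.
- Visit 8: 168 to 196 days after Visit 6, so 315 to 392.
- Visit 9: 337 to 365 days after Visit 6, so 484 to 561.
- Visit 13: 1461 ± 30 days after Visit 6 (48 months), so 1578 to 1687.

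With Visit 6 held common within each ratio:
- Visit 8/Visit 9 (control factor): 315/512 to 392/533 = 0.62 to 0.74.
- Visit 8/Visit 13 (vaccine factor): 315/1638 to 392/1627 = 0.19 to 0.24.
- Visit 9/Visit 13 (ratio between arms): 484/1638 to 561/1627 = 0.30 to 0.34.
- Visit 8/Visit 7 (End of Vaccination): 364/238 to 343/175 = 1.53 to 1.96.

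**Later Visit 10.** SAP 3.1.1 releases the codes only after all subjects complete Visit 8. Assume uniform accrual over 34 − 18 = 16 months (Protocol 3.8 and 3.7). The last Visit 8 is then at calendar Month 16 + 12 = 28, and a child enrolled at month e has Visit 10 at max(18, 28 − e).
- Mean Visit 10: (10/16) × 23 + (6/16) × 18 = 21.1 months. Ratio: 21.1/54 = 0.39.
- Fixed Visit 10 at an assumed Month 24 or 28: 24/54 = 0.44 or 28/54 = 0.52.

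**Incomplete Stage 2.** Assume 80% of vaccinees reach Visit 13 and the rest end at Visit 10.
- Visit 10 at Month 18: 18/(0.8 × 54 + 0.2 × 18) = 18/46.8 = 0.38 pooled; 0.47 as a mean of subject rates.
- Visit 10 as modelled above: 21.1/(0.8 × 54 + 0.2 × 21.1) = 0.45 pooled; 0.51 as a mean of subject rates.

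**If some cutoff replaces End of Study at the primary analysis.** The SAP gives no such rule. Suppose the cutoff is the last Visit 8, with the same accrual. Time on study is 28 − e, mean 20 months. Both arms are multiplied by 12/20 = 0.60 pooled, or 0.64 as a mean of subject rates, and the ratio stays near 1.

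**The case against.** The strongest reply is about timing. All data for variables 2 to 5 end at Visit 8, so they belong to the primary analysis, and no rerun is scheduled. On the timeline above, the last Visit 8 falls at calendar Month 28 and the earliest Visit 13 at Month 54, so no vaccinee would have a Visit 13 date when the rates are first due. This stands as a limit on the arm bias, which arises only if the rates are produced or rerun once End of Study dates exist. It does not rescue the rule, because one of its two dates is then missing for children still on study and no substitute is given.

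A second reply is that the same sentence refers to an observation period, which could mean Visit 1 to Visit 8, and that SAP section 2 leaves programming rules to separate documents. But the stated divisor is days on study, and Table 13 has a row for this study that names other dates. An undefined phrase does not override that.

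Third, enrolment is staged, so uniform accrual is a simplification. If one third enrol in Months 0 to 10 and two thirds in Months 10 to 16 (also an assumption), mean time on study at the cutoff is 28 − (5/3 + 26/3) = 17.7 months and the factor is 12/17.7 = 0.68 instead of 0.60. The size moves; the direction does not.

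Finally, no rate ratio or test is planned on these rates, and the SAE, MAE and NDCMC comparisons use proportions. That is right, and it limits the consequence.

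**Conclusion.** The concern holds. As written, the rule gives wrong rates for variables 2 to 5, because neither permitted end date matches the event window.

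- **End of Study dates:** both arms are understated and the vaccine arm more so. The nominal ratio is 0.33 when the truth is 1.0 (0.30 to 0.34 by visit windows), assuming Visit 10 follows Visit 9 at once and all vaccinees complete Stage 2. Later Visit 10 dates or 80% retention move it to about 0.4 to 0.5.
- **Another on-study cutoff at the primary analysis:** both arms are understated, with little difference between them.
- **End of Vaccination dates:** both arms are overstated about 1.7-fold (1.5 to 2.0 by windows), with a ratio of about 1.

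The damage is confined to supplementary rates reported by group. The primary safety percentages, risk differences and Fisher tests do not use this denominator. Variable 1 is sound if paired with End of Vaccination. This should be fixed before the rates are produced, but it does not threaten the main safety conclusions.

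**What to change.** In SAP 8.2.5.2.7 and Table 13, define days at risk for each variable:

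- **Variable 1:** first vaccination to the end-of-vaccination-phase date. Use the same date that closes the event count in Table 8, because Table 13 allows a later one.
- **Variables 2 to 5:** first vaccination to the Visit 8 date. For a subject without Visit 8, end at the last contact that gave safety information: the call about 6 months after the last dose (Protocol 6.1.11 and 6.1.12) if made, otherwise the withdrawal date. Do not use the Visit 10 or Visit 13 date.
- **Variable 5:** complete its wording, which breaks off before naming the category.

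State whether the group rate is pooled events over person-years or a mean of subject rates, and compute the 95% interval to match.

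A true rate of 1.0 per year is then returned as 1.0 in both arms. The cost is SAP wording and one derived variable, with no new data.
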